Background: Anastomotic leak (Al) is a severe, potentially life-threatening complication following right colectomy. Internationally, anastomotic leak occurs after 8% of right colectomies. Prospective cohort data demonstrate that patient selection, intra-operative factors, and technical variation are risk factors for anastomotic leak. The EAGLE study investigated an educational platform to reduce Al. It showed an absolute reduction in leaks of 20% following implementation and found that in centres where 80% of surgeons undertook the training, the anastomotic leak rate fell by almost 50%. EAGLE 2 is a snapshot audit of centres undertaking the educational intervention to validate the findings from the randomised trial.

Aim: To measure the anastomotic leak rate following right sided large bowel anastomosis in centres where the surgical teams have undertaken the EAGLE platform training.

Design: Prospective audit with clinician derived baseline clinical data and short-term 30-day outcomes for patients undergoing right colectomy and ileocecal resection.

Eligibility: Any hospital or surgical unit performing elective and/or emergency colorectal surgery. Adults (age 18 years and above) undergoing right colectomy or ileocaecal resection for any indication are eligible, including elective, expedited or emergency surgery by open, laparoscopic or robotic approaches.

Primary Outcome measure: 30-day anastomotic leak rate, defined as clinical or radiologically detected anastomotic leak or intra-abdominal or pelvic collection.

Sample size: a consecutive series of cases, collected over an 8 week period, of patients undergoing right sided large bowel anastomosis. The study is open to any centres where the surgical team have undertaken the educational training. These may be centres from EAGLE 1 or new centres that did not take part in EAGLE 1.

BACKGROUND

Clinical problem

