Anastomotic leak has been recognised as a priority research topic by the James Lind Alliance. A comprehensive systematic review and meta-analysis of leak prevention strategies in right colectomy demonstrated a low-quality evidence base to support specific technical and perioperative interventions. Most evidence was based on single-centre observational studies at high-risk of bias. Where randomised studies have been conducted, their interpretation is limited by explanatory designs under-powering, or a lack of contemporary data. International, pragmatic studies are required to improve the evidence base for anastomosis formation, and benefit patients undergoing right colectomy. The 2019 ESCP Hamburg Declaration emphasized the critical importance of addressing unacceptable variation in anastomotic leak rates by quality improvement. The EAGLE 2 audit aims to capture evidence for the beneficial effect of completion of the EAGLE online training to address this variation.

Justification of patient population

Right colectomy is the most commonly performed large bowel resection in the world. It is performed for both acute and chronic conditions, across high, middle and low-income settings. Despite the high risk of anastomotic leak demonstrated in ESCP audits, right colectomy is often considered a simpler and lower-risk operation than left colectomy or rectal surgery, and consequently consultants may not always be the lead surgeon; in selected cases trainees may perform this operation independently. Finally, it is performed by specialist colorectal surgeons and general surgeons.

Rationale for study design

The prospective audit will result in the generation of a large, international dataset of real-world data on the impact of completion of the EAGLE training modules on anastomotic leak rate in centres where most surgeons complete the training.

AIMS & OBJECTIVES

Primary objective

- To measure the anastomotic leak rate following right sided large bowel anastomosis in centres where the surgical teams have undertaken the EAGLE platform training.

Secondary clinical objectives

- To assess the uptake and acceptability of the online training platform.

Primary outcome measure

The primary outcome measure is anastomotic leak within 30-days of surgery (with Day 0 as the day of surgery). The denominator for the primary outcome is the total for patients who had a primary anastomosis. The numerator is anastomotic leak, defined as a composite of either:

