- Anastomotic leakage identified radiologically or clinically
or
- Intraperitoneal (abdominal or pelvic) fluid collection identified radiologically, as per the Centre for Disease Control Criteria for Organ Space infection
or
- Entero-enteric fistula identified radiologically

Secondary outcome measures

- The denominator is the total for patients who had a primary anastomosis:
- Reoperation for anastomotic leak, within 30-days
- The denominator is the total for all patients:
- Reoperation for any cause, within 30-days
- Unplanned admission to critical care, within 30 days
- Readmission within 30 days.
- Post-operative length of hospital stay, up to 30-days
- Mortality within 30-days.
- Rate of ileostomy without anastomosis.
- Rate of defunctioning ileostomy with anastomosis.

Study Design

International prospective audit.

ELIGIBILITY

Hospital inclusion criteria

Any hospital or surgical unit performing elective and/or emergency colorectal surgery. There are no restrictions for hospital/unit size or case volume. Participation in EAGLE 1 is not a pre-requisite.

Participating sites will be expected to recruit all eligible patients within a consecutive 8-week period.

At hospital level, data completeness of 95% will be required to be part of this audit.

Patient inclusion criteria

All adult patients (age 18 years and above) undergoing right colectomy with or without primary anastomosis. Right colectomy is defined as ileocaecal resection or right hemicolectomy (any colonic transection with the distal resection margin proximal to the splenic flexure).

All patients undergoing right colectomy are eligible, including those who do not have an anastomosis and are defunctioned by a proximal stoma.

Procedures for any pathology, via any operative approach (open, laparoscopic, robotic or converted) are eligible.

Elective (surgery on a planned admission), expedited (within 48 hours), and emergency (surgery on an unplanned admission) procedures are eligible.

Patient exclusion criteria

Patients undergoing more than one gastrointestinal anastomosis during the same operation.

In Crohn's disease, additional upstream strictureoplasty or resection/anastomosis to treat disease or strictures at the same operation.

Simultaneous right colectomy and hyperthermic intraperitoneal chemotherapy (HIPEC) and/or cytoreductive surgery.

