| Was anastomotic leak risk calculated intra-operatively ? | Yes / No |
| Has the senior surgeon completed the Safe-anastomosis module? | Yes / No |
| Post-operative data | |
| Post-operative critical care admission | None / Planned from theatre / Unplanned from theatre / Unplanned from ward |
| Total length of hospital stay | Days (up to 30 post-operative days) |
| Anastomotic leak or intra-abdominal/pelvic collection | None / Grade A – requiring no further intervention, radiologically diagnosed / Grade B – requiring radiological reintervention / Grade C – requiring surgical reintervention |
| If yes: How was the leak diagnosed? | Clinical diagnosis only/ Ultrasound imaging/ CT imaging/ MR imaging/ Intra-operative diagnosis |
| Re-operation within 30 days | No / Yes |
| Re-admission within 30 days | No / Yes |
| Mortality within 30 days | No / Yes |

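### The primary outcome is defined in two different ways, and the case report form captures part of the three-component definition incompletely or ambiguously

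*Protocol*

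**What the plan says.** The protocol describes the primary outcome in three places.

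- **Synopsis, Primary Outcome measure:** "30-day anastomotic leak rate, defined as clinical or radiologically detected anastomotic leak or intra-abdominal or pelvic collection". Fistula is not named and no infection criterion is attached to collections.
- **Primary outcome measure section:** a composite of any of three events. The first is "Anastomotic leakage identified radiologically or clinically". The second is "Intraperitoneal (abdominal or pelvic) fluid collection identified radiologically", qualified by "as per the Centre for Disease Control Criteria for Organ Space infection". The third is "Entero-enteric fistula identified radiologically". On the denominator: "The denominator for the primary outcome is the total for patients who had a primary anastomosis".
- **Appendix 1, post-operative data:** a single item, "Anastomotic leak or intra-abdominal/pelvic collection", coded None or one of three grades. The first two grades read "Grade A – requiring no further intervention, radiologically diagnosed / Grade B – requiring radiological reintervention". Grade C is for events needing surgical reintervention. A follow-up item asks how the leak was diagnosed, and its choices include a clinical-only diagnosis and an intra-operative one.

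The secondary outcomes include reoperation because of a leak, and separately reoperation for any cause, both within 30 days. Appendix 1 has one Yes/No item for re-operation, which does not ask the reason.

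**The concern.** The audit's main product is one proportion, so its numerator has to mean the same thing at every site. A site that follows the form exactly meets events that the outcome section counts but the form has no place for, and collections that the form accepts but the outcome section appears to exclude. Each site must then decide alone, and the leak rate becomes partly a product of local coding habit.

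A statistical analysis plan could later choose between the two definitions. It could not recover fields that were never collected. The Data Management section provides central checks for completeness, consistency and compliance, but an event entered as None is a complete and consistent record. It passes the 95% completeness requirement and need not raise a query. Source data and the link to the patient stay at the site, so a later repair would mean sites going back through the notes.

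**Working it through.** The protocol gives no figure to reproduce here. The check is to take each kind of event in a patient with a primary anastomosis and see where each text places it. The qualifier on collections in the outcome section is read as a restriction.

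| Event | Outcome section | Synopsis | Case report form |
|---|---|---|---|
| 1. Leak on imaging, no treatment | Counted | Counted | Grade A |
| 2. Leak on imaging, treated without a procedure | Counted | Counted | Grade A only if intervention means a procedure; otherwise unclear |
| 3. Leak diagnosed clinically, radiological reintervention | Counted | Counted | Grade B |
| 4. Leak diagnosed clinically, surgical reintervention | Counted | Counted | Grade C |
| 5. Leak diagnosed clinically, neither reintervention | Counted | Counted | No grade fits |
| 6. Collection on imaging, criteria met | Counted | Counted | A, B or C, merged with leak |
| 7. Collection on imaging, criteria not met, no leak | Not counted | Counted | A, B or C; criteria not recorded |
| 8. Entero-enteric fistula on imaging | Counted | Not named | No option |

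**Rows 1, 3, 4 and 6** are captured. Grades B and C do not restrict how the event was diagnosed.

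**Row 2** is an ambiguity in Grade A. It does not change the binary outcome so long as the site ticks some grade.

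**Row 5** is a true gap. Grade A requires radiological diagnosis, and B and C each require a reintervention. The form conflicts with itself here, because the next item allows a clinical-only diagnosis.

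**Rows 7 and 8** are where the outcome section and the synopsis disagree. The form follows the synopsis in both.

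**Denominator.** The form records whether the anastomosis was stapled, handsewn or not formed, so the denominator is recoverable.

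**Secondary outcome.** Grade C covers surgical reintervention for a leak or for a collection, and the re-operation item gives no reason. No combination of the two isolates reoperation for a leak.

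**Direction and scale (illustration only).** Let f be the number of true events coded None (rows 5 and 8), and g the number of non-qualifying collections counted (row 7), each as a share of all true composite events. Then

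recorded rate = true rate × (1 − f + g).

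The 8.1% in the Background serves only as a starting value. The documents give no values for f or g, so those below are assumptions.

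- g = 0: f = 2% gives 8.1 × 0.98 = 7.9%; f = 5% gives 8.1 × 0.95 = 7.7%; f = 10% gives 8.1 × 0.90 = 7.3%.
- f = 0: g = 2% gives 8.1 × 1.02 = 8.3%; g = 5% gives 8.1 × 1.05 = 8.5%; g = 10% gives 8.1 × 1.10 = 8.9%.
- f = g: the two cancel and the recorded rate is 8.1%.

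The sign of the net error is therefore unknown.

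**The case against.** The best defence is that the outcome is a composite, so any grade other than None counts, and most leaks and collections will receive one. That is right. A reader might infer that the numerator cannot be counted at all, or that clinically diagnosed leaks have no grade. Neither follows: the gap for clinical leaks is confined to row 5.

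The defence can add that the outcome section makes fistula part of what it calls anastomotic leak, so a site that knows the protocol may enter a fistula in the leak field. A row 5 leak could likewise be put under the nearest grade, and a consistency check might pick up Grade A paired with a clinical-only diagnosis. This stands to the extent that the gap events may, but need not, be coded None. It also concedes the point, since the coding then rests with the site and not with the form.

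On collections, a form label need not repeat a full definition, and a synopsis may be shorter than the text it summarises. That is fair as to wording. But whether the criteria were met is recorded nowhere, so nobody can check later whether sites applied them.

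On separating the components, no component analysis of the primary outcome is planned, so for that outcome alone the merged field would be a matter of preference. It is not so for the secondary outcome. Grade C could stand for reoperation for a leak if leak there means the whole composite, but the protocol does not say so, and fistula would still have no place.

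The missing 30-day label on the leak item is minor, because the outcome definition and the follow-up schedule already fix the window.

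**Conclusion.** The point holds as an inconsistency of definition combined with incomplete capture. Fistula, a clinically diagnosed leak without radiological or surgical reintervention, and a collection that does not meet the organ-space criteria are all left to site discretion. The first two can lower the recorded rate and the third can raise it. The documents give no component frequencies, so neither the size nor the direction of the net error can be estimated, and the figures above show scale only.

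A reader might also infer that the result cannot be compared with the 8.1% from the 2015 audit. The documents do not support that. They do not say how the 8.1% was defined, and the analysis section sets no test against it. Comparability is unverified, not refuted.

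The conclusion rests on reading the organ-space qualifier as a restriction on collections. If it was not meant as one, row 7 falls away and the fistula and clinical-leak gaps remain. Although the gap is narrow, it lies in the single primary outcome and cannot be closed at analysis, so it should be corrected before data are collected.

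**What to change.** 1. Use one definition of the primary outcome in the synopsis, the Primary outcome measure section and Appendix 1, and say whether the organ-space criteria restrict which collections count.
2. Replace the merged item with three Yes/No items, each within 30 days: leak, collection (with a Yes/No for organ-space criteria met), and entero-enteric fistula.
3. Record mode of diagnosis separately from the management grade, so that Grade A no longer depends on radiological diagnosis, and state whether non-procedural treatment counts as intervention for grading.
4. Define the numerator as Yes to any component among patients with a primary anastomosis.
5. Attach the management grade to the component it refers to, so that reoperation for a leak can be told apart from reoperation for a collection.

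The cost is a wording change, an edit to the REDCap form and about three extra tick boxes per patient. If sites have already begun entering data, the records collected so far would need local review of the notes for the new items.

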The audit is designed so that normal patient follow-up pathways can be utilised to obtain outcomes' data. No additional visits or changes to normal follow-up should be made. However, local investigators should be proactive in identifying post-operative events (or lack thereof), within the limits of the follow-up period (30 post-operative day). These may include reviewing the patient notes (paper and electronic) during admission and before discharge to register in-hospital complications, reviewing hospital systems to check for re-attendances or re-admissions, and reviewing post-operative radiology reports, as well as the notes from the in-person outpatient review which we anticipate will occur within the 30 days post-operation in most circumstances.

Data completion and organisation

As EAGLE 2 is an audit, no changes to the normal patient pathway need to be instigated for it to be run.

Data Management

Information will be collected at the following times:

- Short-term follow-up: At baseline (surgeon level)
- At 30 days after the operation (surgeon level). The day of operation will be considered day zero

Data will be entered directly onto the secure electronic REDCap database by study collaborators at the participating hospital sites using pseudonymised data.

Site study collaborators will be provided with a paper copy of the eCRF to facilitate data collection. If this is used, they should then transfer data from the paper CRF into the online database (<https://www.bistc.redcap.bham.ac.uk>). Data management staff will check all incoming data CRFs for completeness, data consistency and compliance with the protocol. If discrepancies or missing data are identified, the data management staff will raise queries with the research team at the participating hospital via the study database.

Source Data

Source data within the EAGLE 2 audit will be kept as part of the participants' medical notes generated and maintained at site. As all data collected and analysed within the EAGLE 2 audit are routinely collected, source data will only be within the medical notes.

Data handling and record keeping

The security of the Study Database System is governed by the policies of the University of Birmingham. The study database will be hosted on the REDCap system managed and maintained by BiCOPS.

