All patients, including those who did not have a primary anastomosis, will be followed-up to a maximum of 30-days post-operatively (with Day 0 being the day of surgery) by a review of their inpatient health records, routine clinic visit letters, and reports for post-operative radiological investigations arranged as part of normal patient care. There will be no additional patient contact (telephone or in-person) beyond what is normal clinical practice at each centre. The study is designed efficiently so that existing patient follow-up pathways and health records can be used, with only data that is routinely collected as part of normal clinical care being captured.

Most anastomotic leaks following ileocolic anastomosis occur in the early post-operative period (days 4-14). Although a small number of anastomotic leaks occur beyond day 30, limiting follow-up to 30 days will ensure that the vast majority of leaks are captured.

Statistical analysis plan

This will be conducted on an intention-to-treat basis i.e. all patients recorded in the database during the scheduled 2-month recruitment periods will be included, and those in the second period will be considered exposed to the intervention regardless of whether learning from the intervention was actually implemented. The primary outcome will be 30-day anastomotic leak rate. In the primary analysis, 30-day leak rate will be modelled using mixed effects logistic regression with random cluster (hospital) effects allowing inclusion of baseline risk factors such as co-morbid disease and ASA score and adjustment for a fixed time effect between time periods.

Sample size

Based on feasibility (below), we assume that if each hospital provides data on 10 patients over a 2-month recruitment period (5 per hospital per month) then adequate sample size will be obtained to allow statistical analysis (see below please).

Projected recruitment

Data for 3,208 right colectomies was submitted by 284 centres over a 2 month period to the 2015 ESCP Right Hemicolectomy Audit; an average of 11.3 patients per 2 months. 81% the sites recruited >10 patients over the 2-month period. A mean of 10 patients per centre is required for each 2 month recruitment period.

| Patients per centre (2 months) | Proportion of centres |
|---------------------------------------|------------------------------|
| 1-5 | 19% (n=53) |
| 6-10 | 37% (n=104) |
| 11-15 | 22% (n=63) |
| 16-20 | 14% (n=39) |
| 21-30 | 6% (n=17) |
| 31+ | 3% (n=8) |

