Planned additional analyses

Pre-planned exploratory sub-group analyses of the primary outcome will be performed in the following groups:

- *At cluster (hospital) level:*
- Number of beds (<500 versus ≥500 total hospital beds).
- Right colectomy volume (<10 patients versus ≥10 patients per 2 month period).
- Early adoption (early versus late study entrants).
- Health service expenditure per capita in purchasing parity (top versus middle versus bottom tertile).
- Proportion of operating surgeons in each centre completing the online training modules prior to 'post-implementation' data collection (high [≥80%], intermediate [50-79%], low [<50%]).
- World Bank income group (high versus middle/low-income country).

At patient level:

- Indication for surgery (malignant versus benign, e.g. inflammatory bowel disease).
- Procedure urgency (elective versus expedited/ emergency).
- Age (≤65 years versus >65 years).
- Operative approach (open versus laparoscopic/ robotic).
- Anastomotic technique (stapled versus handsewn anastomosis).
- Primary operating surgeon experience as reported (trainee versus consultant).
- Primary operating surgeon specialism as reported (general versus colorectal surgeon).
- Reverse analysis will also be undertaken to explore what are the characteristics of hospitals with a big change versus no change, and do these differ in respect of cluster characteristics.

STUDY ORGANISATIONAL STRUCTURE

EAGLE 2 Audit Office

The coordinating centre for EAGLE 2 is based at the University of Birmingham in the Birmingham Centre for Observational and Prospective Studies (BiCOPS). Members of this group also represent the European Society of Coloproctology (ESCP) and sit on both the research committee and cohort studies committee of ESCP.

Local teams

We envisage that most hospitals opening for the audit will identify a team of up to 5 members, which may include surgical colleagues, trainee doctors, nurses, medical students, or others involved in the routine clinical care of eligible patients, depending on local circumstances. Members of this group will be responsible for the local conduct of the audit at their site, including helping to identify potential patients and record data onto the EAGLE 2 REDCap database.

Publication policy

The output from this research will be published under a single corporate authorship group: “European Society of Coloproctology (ESCP) collaborating group”.

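### The primary leak outcome includes imaging-only events, but scan status is not recorded for patients without a leak, so the income and expenditure subgroups may partly reflect how much hospitals scan

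*Protocol*

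**What the plan says.** The Protocol (Primary outcome measure) builds the numerator from three components: "Anastomotic leakage identified radiologically or clinically"; "Intraperitoneal (abdominal or pelvic) fluid collection identified radiologically, as per the Centre for Disease Control Criteria for Organ Space infection"; and "Entero-enteric fistula identified radiologically". The denominator is patients with a primary anastomosis.

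The CRF in Appendix 1 grades the event. Its lowest positive grade is "Grade A – requiring no further intervention, radiologically diagnosed". Grades B and C are events that needed radiological or surgical re-intervention.

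No imaging is prescribed. Under Data collection the rule is "No additional visits or changes to normal follow-up should be made", and under Data collection and follow-up the source is "reports for post-operative radiological investigations arranged as part of normal patient care". The only post-operative imaging item on the CRF is conditional on an event: "If yes: How was the leak diagnosed".

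Planned additional analyses lists exploratory subgroups of the primary outcome. They include "World Bank income group (high versus middle/low-income country") and tertiles of health expenditure per head. Publication policy offers each unit its own results for benchmarking. The model in the Statistical analysis plan section has a random hospital effect and baseline risk factors, and it names no imaging variable.

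**The concern.** A Grade A event exists in the data only if someone ordered a scan. Two groups of hospitals with the same true frequency of anastomotic failure, but different use of imaging, will therefore record different leak rates, and the group that looks less will appear better.

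The comparisons most exposed are those by country income and health expenditure, because access to imaging plausibly differs along those lines. The protocol itself describes the operation as done in high-, middle- and low-income settings.

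The CRF gap matters because analysis cannot close it. If scan status is never collected for patients coded as having no leak, imaging rates cannot be compared between groups, and nobody can check afterwards whether a difference in leaks follows a difference in scanning.

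**Working it through.** **Step 1: facts from the documents.**

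- Two of the three outcome components (collection, fistula) count only on imaging. The third (leak) counts on imaging or clinical grounds.
- Grade A is a positive category and requires a radiological diagnosis.
- Imaging follows local usual care.
- The CRF records the mode of diagnosis only when an event is present.

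The CRF wording adds a second route in the same direction. A leak diagnosed clinically, never imaged and needing no radiological or surgical re-intervention meets the outcome definition. It fits none of Grades A, B or C as worded, although the CRF does offer clinical diagnosis as a mode.

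**Step 2: size.** The protocol gives no figure to reproduce on this point. Inputs for an illustration:

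- p = 8.1%, the leak rate in the 2015 ESCP audit (Protocol, Existing international data), taken as the true rate in both groups and fully detected in the higher-imaging group.
- g = share of events that are Grade A. Not in the documents; assumed 10% to 40%.
- r = chance that a Grade A event is found in the lower-imaging group, relative to the higher-imaging group. Not in the documents; assumed 0.75 to 0.25.
- Grades B and C are taken as equally well detected in both groups.

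Recorded rate in the lower-imaging group = p × [(1 − g) + g × r]. The relative reduction is g × (1 − r), whatever the value of p.

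| g | r = 0.75 | r = 0.50 | r = 0.25 |
|---|---|---|---|
| 10% | 7.9% | 7.7% | 7.5% |
| 20% | 7.7% | 7.3% | 6.9% |
| 30% | 7.5% | 6.9% | 6.3% |
| 40% | 7.3% | 6.5% | 5.7% |

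The smallest spurious relative reduction is 0.10 × 0.25 = 2.5% (odds ratio 0.97). The largest is 0.40 × 0.75 = 30% (odds ratio 0.68).

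**Step 3: what the model can do.** A random hospital effect absorbs unexplained variation between hospitals. It does not remove a systematic difference in detection between income or expenditure groups, because that difference goes into the group coefficient.

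**Step 4: the existing secondary outcome.** Return to theatre for a leak corresponds roughly to Grade C and depends far less on scanning. It leaves out Grade B, and the subgroup analyses are specified for the primary outcome only.

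**Step 5: precision of a Grade B/C outcome.** If 75% of events are Grade B or C (assumed), relative intervals widen by a factor of about 1/√0.75 = 1.155, or about 15%.

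**The case against.** The strongest reply is that this is a routine-data audit whose main aim is to measure a leak rate in trained centres. Uneven ascertainment comes with that design, and the comparisons at risk are labelled exploratory. This stands, and it limits the point to interpretation of those subgroups and of benchmarking.

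A reader might infer more than the documents support:

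- *That the primary leak rate is invalid.* It remains a fair description of leaks recorded under usual care. The problem arises when groups with different scanning habits are compared.
- *That the artefact rivals the 20% effect reported for EAGLE.* That figure concerns training, not a contrast between hospitals that scan more and less. A reduction as large as 20% also needs assumptions in the upper part of the grid (for example g = 40%, r = 0.50). At g = 10% and r = 0.75 the rate moves only from 8.1% to 7.9%.
- *That every hospital-level subgroup is affected.* A plausible link to imaging access exists for income and expenditure. The documents give no reason why bed numbers, volume or training share should follow scanning.
- *That incidental findings on scheduled scans inflate the numerator.* No scans are scheduled, usual-care imaging includes scans for clinical suspicion, and collections are tied to organ-space infection criteria.

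It can also be said that a Grade B/C analysis needs no new data and may sit in a statistical analysis plan that is not shown. That is true of the analysis, and its absence here is not counted as an error. It is not true of scan status, which the CRF in this protocol does not collect.

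Investigators are asked to be proactive in reviewing radiology reports, but a scan that was never done leaves no report.

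**Conclusion.** The point holds in a limited form. Imaging-only events count, imaging follows local practice, and scan status in patients without a recorded event is unknown. Other things equal, groups that scan less will record fewer leaks. This chiefly affects the exploratory comparisons by World Bank income group and health expenditure, and benchmarking between units.

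The direction follows from the definitions, provided that some events are Grade A and that detection differs between the groups. The size does not follow: the range of 2.5% to 30% rests wholly on assumed Grade A shares and detection ratios. It is an inexpensive improvement worth making, not a flaw in the primary objective.

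**What to change.** 1. Add one CRF item for all patients: post-operative abdominal or pelvic imaging within 30 days (none / ultrasound / CT / MR), and whether it was done for clinical suspicion. Report imaging rates by income and expenditure group, including among patients without a leak.
2. In the hospital- and country-level comparisons under Planned additional analyses, report leak or collection of Grade B or C beside the primary outcome, with the primary-anastomosis denominator. Interpret a difference cautiously if it is confined to Grade A or follows imaging rates.

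Do not adopt a rule that a difference is real when both outcomes point the same way. Grade B/C is nested in the primary outcome. If 75% of events are B/C, the correlation is about √0.75 = 0.87, and with no true difference the two directions agree with probability 1/2 + arcsin(0.87)/π, about 83% (normal approximation). Such a rule would screen out little.

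The cost is one extra field, filled from radiology reports that investigators already review, with no added scan, visit or patient contact. The added outcome has fewer events. Imaging rates will be partly confounded by indication, since patients are often scanned because a leak is suspected. Grade B will still depend partly on access to interventional radiology. The primary outcome does not change.
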